## **1. STUDY SUMMARY**

### **Background**

Diabetes mellitus, especially Type 2 Diabetes Mellitus (T2DM), is a growing public health problem worldwide. Individuals newly initiated on insulin therapy often experience increased anxiety and decreased treatment adherence. Game-based educational methods have been shown to improve motivation, reduce anxiety, and enhance learning. This study evaluates the effect of a specially designed board game, "Let's Learn Diabetes," on treatment adherence and anxiety levels.

### **Objective**

To determine whether game-based education improves treatment adherence and reduces anxiety levels in patients with Type 2 Diabetes who have recently started insulin therapy.

### **Hypotheses**

- H1: Game-based diabetes education will significantly improve treatment adherence levels.
- H2: Game-based diabetes education will significantly reduce anxiety levels.

## **2. STUDY DESIGN**

This is a randomized controlled trial (RCT) with pre-test and post-test measures.

- Groups: Intervention group (game-based education) and Control group (traditional education).
- Duration: 1 month of active intervention followed by a 1-month follow-up.
- Randomization: Participants will be randomly assigned to either the intervention or control group.

## **3. STUDY POPULATION**

### **Inclusion Criteria:**

- Age between 40-65 years.
- Diagnosed with Type 2 Diabetes for at least 1 year.
- Initiated insulin therapy within the last 3 months.
- No diagnosed mental health disorders.
- Voluntary participation with signed informed consent.

**Exclusion Criteria:**

- Age below 40 or above 65 years.
- On insulin therapy for more than 3 months.
- Mental or psychological comorbidities.
- Declining to participate or incomplete participation in all four sessions.

**Study Site**

Uşak Training and Research Hospital Diabetes Education Unit and Diabetes School.

**4. SAMPLE SIZE**

The sample size was calculated using G\*Power 3.1.9.2 at a 95% confidence level, effect size 0.768, and power of 85%.

- Minimum required per group: 32 participants
- Total sample size: 72 participants (36 in each group)

**5. STUDY PROCEDURES****Intervention Group:**

- Participants will attend four 2-hour game-based education sessions, once per week for 1 month.
- Game sessions will be conducted using the "Let's Learn Diabetes" board game, which includes three difficulty levels.

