**Control Group:**

- Participants will receive traditional diabetes education through lectures and presentations for the same duration.

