## **10. STUDY TIMELINE**

- Recruitment: May 2024 - October 2024
- Intervention: October 2024
- Data Collection: November 2024
- Analysis and Reporting: December 2024 - March 2025

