### Primary Outcome Analyses

- Within-group analysis: Paired t-test comparing pre-test and post-test scores for anxiety and adherence.
- Between-group analysis: Independent t-test comparing post-test mean differences between intervention and control groups.

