## **SIGNIFICANCE LEVEL**

- All statistical tests will be two-tailed, with a significance threshold of  $p < 0.05$ .

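### If sessions are shared, as the documents strongly suggest but never state, the independent t-test ignores correlation within session groups and its type I error can exceed 5%

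*Combined protocol and SAP*

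**What the plan says.** Participants are individually randomised (protocol section 2). For the intervention arm, section 5 states: "Participants will attend four 2-hour game-based education sessions, once per week for 1 month". The sessions use a board game. Controls receive "traditional diabetes education through lectures and presentations for the same duration". The site is a hospital diabetes education unit and Diabetes School (section 3, Study Site). The timeline in section 10 has recruitment from May to October 2024 but gives "Intervention: October 2024" for delivery.

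The SAP's primary between-arm analysis is an "Independent t-test comparing post-test mean differences between intervention and control groups". Under Normality and Assumptions, the SAP checks normality and equal variances and falls back on the Mann-Whitney U test. Independence is not discussed. Under Significance Level: "All statistical tests will be two-tailed, with a significance threshold of" p below 0.05.

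Section 4 computes the sample size "at a 95% confidence level, effect size 0.768, and power of 85" per cent. It gives "Minimum required per group: 32 participants" and plans 36 per arm. It contains no ICC or design effect.

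Neither document says whether sessions are individual or shared. Group size, number of groups, how groups are formed and number of educators are also missing, and no analysis includes a term for session group or educator.

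**The concern.** People who spend four two-hour sessions at the same table or in the same class share an educator, a pace and a group mood. Anxiety and adherence could both be affected, so post-test scores within a session group may be positively correlated even though individuals were randomised. The t-test and the Mann-Whitney test would then count 36 independent observations per arm when there are effectively fewer. For both primary outcomes the confidence intervals would be too narrow, the p-values too small and the power overstated.

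**Working it through.** **1. The plan's own figure.** Inputs from section 4: d = 0.768 (so SD = 1), power 85%. Alpha is 0.05 two-sided (SAP, Significance Level). The power of a two-sample t-test uses the noncentral t with noncentrality d√(n/2) and 2n − 2 degrees of freedom:

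- n = 31: 84.5%
- n = 32: noncentrality 0.768 × √16 = 3.07, power 85.6%
- n = 36: noncentrality 0.768 × √18 = 3.26, power 89.5%

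The stated minimum of 32 is reproduced, under independence.

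**2. Is one-to-one delivery credible?** Individual teaching needs 36 × 4 × 2 = 288 contact hours per arm, 576 in total. October 2024 has 23 weekdays, so 576 / 23 ≈ 25 hours per weekday at one unit. Pairs would need about 12.5 hours, groups of 3 about 8.3 and groups of 4 about 6.3. Shared sessions are therefore likely, but the sum does not reveal the group size, and staffing is not given.

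**3. Effect of clustering.** Group size m and ICC are assumptions, with equal, fixed groups in both arms and 36 per arm.

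- Design effect: DE = 1 + (m − 1) × ICC
- True SE divided by t-test SE: about √DE
- Type I error: about 2 × [1 − Φ(1.96/√DE)], checked by simulating the ordinary t-test 50,000 times per setting
- Power of an unadjusted t-test on group means: noncentrality d√(36/(2·DE)), degrees of freedom 2k − 2, with k groups per arm

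| m (k per arm) | ICC | DE | SE ratio | Type I, formula | Type I, simulated | Power, group means |
|---|---|---|---|---|---|---|
| 4 (9) | 0 | 1.00 | 1.000 | 5.0% | 4.9% | 86.4% |
| 4 (9) | 0.01 | 1.03 | 1.015 | 5.3% | 5.2% | 85.4% |
| 4 (9) | 0.05 | 1.15 | 1.072 | 6.8% | 6.7% | 81.4% |
| 6 (6) | 0.05 | 1.25 | 1.118 | 8.0% | 7.9% | 74.8% |
| 9 (4) | 0.05 | 1.40 | 1.183 | 9.8% | 9.8% | 63.4% |
| 12 (3) | 0.05 | 1.55 | 1.245 | 11.5% | 11.7% | 51.1% |
| 12 (3) | 0.10 | 2.10 | 1.449 | 17.6% | 18.0% | 40.5% |

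Worked row (m = 6, ICC 0.05): DE = 1 + 5 × 0.05 = 1.25; √1.25 = 1.118; 1.96/1.118 = 1.753; two-sided tail 0.080.

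**4. Margin in the plan.** 36/32 = 1.125. With groups of 6 that design effect is reached at ICC = 0.125/5 = 0.025. This assumes no dropout and ignores the loss of degrees of freedom from having few groups.

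**The case against.** The strongest reply is that the documents never mention groups. The contact-hours sum assumes one teaching stream and relies on a single timeline line. Membership may also change from week to week, whereas the calculation assumes fixed groups. All of this stands. A reader might infer that both arms are certainly taught in groups and that the error rate certainly exceeds 5%. The documents do not support that, because both the delivery format and the ICC are unknown. With small groups and an ICC near zero the inflation is negligible.

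A reader might also infer that the 85% power is wrong, or holds only at zero ICC. Neither follows. The arithmetic is correct, and 36 per arm gives 89.5% under independence, so 85% survives a small positive ICC. The group-mean power figures above come from an unadjusted test. A baseline-adjusted analysis would do better: with an assumed pre/post correlation of 0.5, which the documents do not give, simulated power was 93% (groups of 4, ICC 0.02), 86% (groups of 6, ICC 0.05) and 76% (groups of 9, ICC 0.05).

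Finally, a mixed model has limits with few groups. In unadjusted simulations of those three settings, the group variance was estimated as zero in roughly 33 to 45% of trials. If an arm is taught as one class, the model cannot help at all. These points shape the fix but do not remove the gap.

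**Conclusion.** The point holds conditionally. It is certain that the primary test, its fallback and the sample size assume independent participants, and that nothing in the plan addresses session group or educator. It is likely, but unstated, that sessions are shared. If they are, and the ICC is positive, the planned t-test understates the standard error. Under the assumed settings its type I error runs from about 5.3% (groups of 4, ICC 0.01) through about 8% (groups of 6, ICC 0.05) to about 18% (groups of 12, ICC 0.10, which pairs a large group with a large ICC). With zero ICC, or one-to-one delivery and no educator effect, it stays at 5%. The sample size is not miscalculated, but its margin covers a design effect of only about 1.125 with no dropout. The change is worth making because it is cheap and protects both primary comparisons.

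**What to change.** - **Section 5.** State for each arm whether sessions are individual or shared, the group size, the number of groups, whether membership is fixed, and the number of educators. Record a session-group ID and an educator ID for every participant.
- **SAP, Primary Outcome Analyses.** Replace the independent t-test as the primary between-arm analysis with a linear mixed model of post-test score. Use arm and pre-test score as fixed effects, a random intercept for session group and Satterthwaite degrees of freedom. SPSS can fit this. With one-to-one delivery it reduces to ANCOVA. Say in advance what is done if the group variance is estimated as zero. A t-test on group means is a suitable sensitivity analysis; its simulated type I error was 4.9 to 5.2%.
- **Section 4.** Say that the calculation assumes independent participants (85.6% power at 32 per arm, 89.5% at 36) and that 36 against 32 covers a design effect of only about 1.125 with no dropout. Give power for the planned group size over an ICC range, for example 0.02 to 0.10.
- **Design.** Use at least several groups per arm. One class or one educator per arm is confounded with treatment, and no model can separate the two. If that is the design, state it as a limitation.

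The cost is two data fields, some tracking of group membership (make-up sessions become harder to place if groups are kept fixed), somewhat wider intervals, fewer degrees of freedom and a less favourable stated power. No extra participants are needed for the analysis change itself.

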**Control Group:**

- Participants will receive traditional diabetes education through lectures and presentations for the same duration.

**Follow-up:**

- Post-test measurements will be collected one month after completion of the intervention.

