## **7. DATA COLLECTION**

Data will be collected at two time points:

Pre-test: Before the first intervention session.

Post-test: After the final session.

Instruments:

- Beck Anxiety Scale (BAS)
- Patient Compliance Scale for Type 2 Diabetes Mellitus Treatment

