# STATISTICAL ANALYSIS PLAN

## STATISTICAL ANALYSIS PLAN (SAP)

- Intention-to-Treat (ITT): Includes all randomized participants who completed at least one session.
- Per-Protocol (PP): Includes only participants who completed all four sessions.

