## **HANDLING DROPOUTS**

- Participants who miss one or more intervention sessions will be excluded from the Per-Protocol analysis but included in the Intention-to-Treat analysis if they completed pre-test measurements.

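### The single post-baseline measurement is tied to course events and is not scheduled for patients who stop early, so the Intention-to-Treat analysis can shrink towards those who reached the end of the course

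*Combined protocol and SAP*

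**What the plan says.** Protocol section 7 states: "Data will be collected at two time points". One is the pre-test, so each patient has a single post-baseline measurement. It is dated in two ways, both by reference to the course. Section 5, Follow-up: "Post-test measurements will be collected one month after completion of the intervention". Section 7: "Post-test: After the final session". Section 2 gives the overall shape ("Duration: 1 month of active intervention followed by a 1-month follow-up"), and section 10 puts the intervention in October 2024 and data collection in November 2024 for the trial as a whole.

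On patients who do not finish, the documents point in different directions:

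- Protocol section 3 lists as an exclusion criterion: "Declining to participate or incomplete participation in all four sessions".
- The opening section of the SAP defines the Intention-to-Treat set thus: "Includes all randomized participants who completed at least one session".
- The SAP section on handling dropouts says that patients who miss sessions are "included in the Intention-to-Treat analysis if they completed pre-test measurements".
- The SAP data management section applies listwise deletion to missing data in the final analyses.

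No section says whether or when a patient who stops early completes the two questionnaires.

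**The concern.** Finishing the course and attending its last session both happen after randomisation. A patient who stops after the first, second or third session reaches neither, so staff who follow sections 5 and 7 literally have no date on which to measure that patient. The section 3 exclusion, which can be judged only once the course has run, gives them a written reason not to try.

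The SAP keeps such patients in the Intention-to-Treat set, but the between-group t-test needs a post-test value and listwise deletion removes anyone without one. Who is analysed may then be settled at data collection. The arms receive different teaching formats (board game versus lectures), so stopping could plausibly depend on the arm. In that case a comparison restricted to those who reached the end no longer has the protection of randomisation, for anxiety or for adherence. A different missing-data method would not repair this, because it would rest on assumptions about outcomes that nobody tried to collect. Settling the disagreement between sections 5 and 7 on timing would not repair it either, because both timings depend on the course.

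**Working it through.** **1. Side-by-side reading, for a patient who attends two sessions and stops**

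| Place | Consequence |
|---|---|
| Protocol section 5, Follow-up | Due date runs from completing the intervention; none defined for this patient unless completion means the scheduled course end |
| Protocol section 7 | Due date follows the final session; same gap |
| Protocol section 3, exclusions | Falls under an exclusion criterion |
| SAP, Intention-to-Treat definition | Included (at least one session attended) |
| SAP, handling dropouts | Included (if the pre-test was done) |
| SAP, primary outcome analyses | A post-test value is needed |
| SAP, data management | Deleted if that value is missing |

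The patient is in the Intention-to-Treat set by definition but contributes to the analysis only if someone collects a post-test that no section schedules.

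**2. The plan's own sample size**

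Inputs: effect size 0.768 (taken as a standardised mean difference d), power 85%, 95% confidence level, minimum 32 and planned 36 per group (protocol section 4); two-sided tests (SAP, significance level).

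Power for n per arm uses the noncentral t distribution with 2n − 2 degrees of freedom, noncentrality d × √(n/2) and two-sided alpha 0.05.

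- n = 31: 84.5%
- n = 32: 85.6%, the smallest n reaching 85%, so the plan's figure of 32 is reproduced
- n = 36: 89.5%

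**3. Power under loss**

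Assumptions: equal loss in both arms, no post-test in those lost, d unchanged. Analysed n = 36 × (1 − loss).

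| Loss per arm | n per arm | Power |
|---|---|---|
| 0% | 36 | 89.5% |
| 5% | 34.2 | 87.9% |
| 10% | 32.4 | 86.1% |
| 15% | 30.6 | 84.0% |
| 20% | 28.8 | 81.7% |
| 30% | 25.2 | 76.2% |

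The margin down to the stated minimum is (36 − 32)/36 = 11.1%. Interpolating between n = 31 and n = 32, power equals 85% at n ≈ 31 + (85.0 − 84.5)/(85.6 − 84.5) ≈ 31.4, a loss of (36 − 31.4)/36 ≈ 13%. Power therefore drops below plan once loss passes about 11% to 13%.

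**4. Bias from analysing only those measured**

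In each arm, the mean of those measured exceeds the mean of all randomised by (share who stop) × (deficit of stoppers against finishers). The bias in the between-arm difference is:

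bias = p(game) × deficit(game) − p(control) × deficit(control)

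The documents give neither quantity. Illustrations:

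- Same share stopping and same deficit in both arms: 0.
- 20% versus 10% stopping, deficit 0.5 SD in both: 0.20 × 0.5 − 0.10 × 0.5 = 0.05 SD, or 0.05/0.768 = 6.5% of the planned effect.
- Same stopping rates, deficit 0.5 SD in the game arm only: 0.20 × 0.5 − 0 = 0.10 SD. This needs deficits that differ by arm, which nothing in the documents supports.

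**The case against.** The strongest reply is that the documents are silent here and do not bar anyone from being measured. Completion of the intervention can mean the scheduled end of the course. Section 2 describes a fixed month of teaching plus a fixed month of follow-up, and section 10 places teaching in October and data collection in November 2024 for everyone. Keeping patients who miss sessions in the Intention-to-Treat set makes little sense unless their outcomes are to be collected. This stands to the extent that a reader might infer that early stoppers are never due a post-test, and the text does not say so. But sections 2 and 10 set no due date or window for the individual patient, and neither says that non-attenders are measured. If a fixed date is intended, a sentence would confirm it.

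Three other stronger inferences also fail:

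- **That the Intention-to-Treat set must collapse to the Per-Protocol set.** A patient who misses the second session but attends the fourth reaches the final session, so is due a post-test under section 7. For the same reason, the chance of attending all four sessions should not be used as the share measured; that would overstate the loss of power.
- **That the time to post-test drifts for patients who finish late.** No section provides for late or make-up sessions, and the sessions are weekly within one month.
- **That patients have no other outcome data.** A pre-test is taken; what may be missing is the only post-baseline value.

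**Conclusion.** The concern holds as a gap in the data-collection rule with a real consequence. The only post-baseline measurement is anchored to course events, no section schedules it for those who stop early, the exclusion list counts incomplete attendance against them, and listwise deletion removes those without a value. Followed literally, the plan can turn the promised Intention-to-Treat comparison into one of patients who reached the end of the course.

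The size is uncertain because no stopping rate is given. Loss up to about 11% per arm is covered by the planned 36; at 20% the shortfall is about three percentage points below the planned 85%. Bias matters more than power, since it affects both primary outcomes and cannot be removed afterwards without untestable assumptions. Under the illustrated unequal stopping with equal deficits it is modest, at about 0.05 SD. At those stopping rates, 0.10 SD would need a deficit in the game arm only. The change is worth making because it is cheap and the missing data could not be recovered later.

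**What to change.** 1. In protocol sections 5 (Follow-up) and 7, date the post-test from the scheduled date of the patient's fourth session, plus whichever interval the sponsor keeps, with the same window in both arms. The two sections should then agree.
2. State there that the post-test is collected from every randomised patient regardless of sessions attended, and that those who stop are contacted to complete the two questionnaires.
3. Remove incomplete attendance from the exclusion criteria in section 3, so that it defines only the Per-Protocol set. Without this step, changing sections 5 and 7 would leave the exclusion in force for the same patients.
4. Replace the two differing Intention-to-Treat rules in the SAP (at least one session attended; pre-test completed) with one definition, preferably all randomised patients analysed as allocated.

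The cost is a few sentences and a few extra contacts, with no new instrument. Some early stoppers will still not be reached, so some missing data will remain.

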**6. OUTCOME MEASURES****Primary Outcomes:**

1. Anxiety level measured by Beck Anxiety Scale (BAS).
2. Treatment adherence measured by the Patient Compliance Scale for Type 2 Diabetes Mellitus Treatment.

Secondary Outcomes:

- Sub-dimension scores of the treatment adherence scale, including emotional factors, knowledge factors, lifestyle changes, and diet-related factors.

## **7. DATA COLLECTION**

Data will be collected at two time points:

Pre-test: Before the first intervention session.

Post-test: After the final session.

Instruments:

- Beck Anxiety Scale (BAS)
- Patient Compliance Scale for Type 2 Diabetes Mellitus Treatment

## **8. STATISTICAL ANALYSIS**

- Statistical analyses will be conducted using SPSS version 25.0.
- Descriptive statistics: mean, standard deviation, frequency, and percentage.
- Independent t-tests will be used for between-group comparisons.
- Paired t-tests for within-group comparisons.
- Pearson correlation for relationships between anxiety and adherence.
- Significance level set at  $p<0.05$ .
- Cronbach's alpha will be used to assess the reliability of scales.

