### Secondary Outcome Analyses

- Pearson correlation to examine relationships between anxiety levels and sub-dimensions of treatment adherence.
- Subgroup analyses by demographic factors (age, gender, education level).

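### The anxiety–adherence correlation names neither time point nor arm handling; run over both arms on post-treatment scores, it would mix the treatment effect into the coefficient

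*Combined protocol and SAP*

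**What the plan says.** Protocol section 8 (Statistical Analysis) lists a "Pearson correlation for relationships between anxiety and adherence". The SAP, under Secondary Outcome Analyses, has "Pearson correlation to examine relationships between anxiety levels and sub-dimensions of treatment adherence". Neither line names a time point, an arm or an adjustment, and no partial or stratified correlation appears elsewhere in either document.

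Three other places bear on this:

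- Protocol section 1 (Hypotheses). H1 predicts better adherence with the game. H2 states: "Game-based diabetes education will significantly reduce anxiety levels".
- Protocol section 7 (Data Collection). There are two measurement occasions, one before the first session and one after the last.
- SAP, Significance Level. "All statistical tests will be two-tailed, with a significance threshold of" p < 0.05, so each correlation will be read as significant or not.

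**The concern.** By the trial's own hypotheses, treatment arm is a common cause of both variables after randomisation. If the game lowers anxiety and raises adherence relative to lectures, the intervention arm sits towards low anxiety and high adherence and the control arm towards the opposite. A coefficient over all participants then picks up the distance between the two arm means as well as any relation among patients treated alike.

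What is at stake is interpretation. A report could say that less anxious patients adhere better when part of the coefficient, or all of it if the within-arm relation is nil, comes from the difference between arms. Protocol section 6 names four adherence sub-dimensions, so the issue could recur in several tests.

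**Working it through.** **Inputs from the documents**

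- Planning values (protocol section 4): "at a 95% confidence level, effect size 0.768, and power of 85" per cent.
- Group sizes (protocol section 4): "Minimum required per group: 32 participants", and "Total sample size: 72 participants (36 in each group").
- Sidedness (SAP, Significance Level): two-sided.
- Direction of effect (protocol section 1): anxiety down, adherence up.

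**Assumptions not in the documents**

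- The same standardised shift d applies to both scales. Section 4 does not say which scale 0.768 belongs to, so a range of d is shown.
- Within-arm SDs are equal across arms, scores are bivariate normal, and there is no dropout.
- The within-arm correlation rho is not given; 0, −0.2 and −0.3 are tried.
- A higher adherence score means better adherence. This affects only the sign.

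**Step 1: the plan's own figure.** For a two-sided 5% t-test with d = 0.768 and 85% power, the exact noncentral-t calculation gives 32 per group (power 0.856), which matches the protocol. With 36 per group the power is 0.895. The stated inputs are therefore read correctly. The plan gives no figure for the correlation.

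**Step 2: what pooling adds.** Work in within-arm SD units with 1:1 allocation. A shift d between arms adds d²/4 to the variance of a score pooled over arms. Opposite shifts d1 (anxiety down) and d2 (adherence up) add −d1·d2/4 to the covariance. Hence

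pooled r = (rho − d1·d2/4) / √[(1 + d1²/4)(1 + d2²/4)].

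With rho = 0:

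- d = 0.5 on both: −0.0625 / 1.0625 = −0.059
- d = 0.768 on both: 0.768²/4 = 0.1475, so −0.1475 / 1.1475 = −0.129
- d = 1.0 on both: −0.25 / 1.25 = −0.20
- 0.768 on one scale and 0 on the other: the numerator is 0, so r = 0
- d = 0 on both (pre-test): r = 0

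With a real within-arm relation and d = 0.768 on both:

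- rho = −0.2: (−0.2 − 0.1475) / 1.1475 = −0.30
- rho = −0.3: (−0.3 − 0.1475) / 1.1475 = −0.39

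**Step 3: how often the test rejects.** At N = 72 the two-sided 5% critical value of r is 0.232 in size. Simulation (40,000 trials per case, 36 per arm, rho = 0) gives:

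| Shift on the two scales | Expected pooled r | Pooled test rejects | Arm-adjusted test rejects |
|---|---|---|---|
| 0 and 0 | 0.00 | 4.8% | 4.9% |
| 0.5 and 0.5 | −0.06 | 7.9% | 5.1% |
| 0.768 and 0.768 | −0.13 | 18.7% | 5.0% |
| 1.0 and 1.0 | −0.20 | 40.5% | 5.0% |
| 0.768 and 0 | 0.00 | 4.9% | 4.9% |

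In every row the mean arm-adjusted correlation is 0.00 to two decimals.

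**The case against.** The strongest reply is that the documents never commit to the analysis that causes the trouble.

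- **A reader might infer that the plan pools the arms at post-test.** The within-group t-tests are labelled as such and the correlation is not, which makes one overall coefficient a natural way to carry it out. But the text does not say so. Separate coefficients by arm, or a pre-test correlation, fit it equally well, and at pre-test randomisation leaves no treatment effect to mix in. This objection stands: the fault is an unstated choice.
- **A reader might infer that the coefficient would simply be the treatment effect under another name.** That holds only if the within-arm correlation is exactly zero, which nothing in the documents supports. With rho = −0.3 the pooled value is −0.39: a real association, moderately inflated.
- **A reader might infer that the test fails to hold its 5% level.** A pooled Pearson test addresses the overall correlation. If both means shift, that correlation is not zero, and rejecting is correct for that null. The 19% is an error rate only for the null of no within-arm association, which the plan does not state. The plan states no null for the correlation at all, so the within-arm null is this review's choice.
- **The size is uncertain.** The comparator is active education of the same duration, so the between-arm shift may be small, and the induced correlation falls roughly with d². The SAP correlates anxiety with sub-scores, for which no effect size is given, so the figures illustrate that analysis and do not predict it.

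What survives is the mechanism. If both scores move, as H1 and H2 predict, an unadjusted coefficient over both arms after treatment mixes two sources of association, and the plan does nothing to prevent it.

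**Conclusion.** The point holds as a minor specification gap with a conditional bias. Three conditions are needed together: both arms in one coefficient, post-test or change scores, and movement on both scales. Under the assumptions listed with the calculation, the spurious component ranges from about 0.06 (d = 0.5) to 0.20 (d = 1.0) in size. At d = 0.768 it is 0.13, and a within-arm correlation of 0.20 in size becomes about 0.30.

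The correlation is secondary in the SAP. It tests neither H1 nor H2, and it has no bearing on the between-group comparison or the sample size. The correction is worth making because it is nearly free, not because the trial's main conclusion is at risk.

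**What to change.** Amend protocol section 8 and the SAP's Secondary Outcome Analyses to:

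1. Name the time point of each correlation.
2. For post-test scores, use a partial correlation of anxiety with adherence (and with each sub-score) controlling for arm, or report the correlation separately by arm.
3. Keep the unadjusted Pearson correlation for pre-test data only.
4. Give 95% confidence intervals and label these analyses exploratory.

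Change scores are not required. They ask how the changes relate rather than how the levels relate, and adjusting for arm does not depend on them. If they are used, the same arm adjustment applies.

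The cost is wording and one degree of freedom, with no new data. The single partial correlation assumes a similar within-arm correlation in both arms. Reporting by arm avoids that assumption but is less precise. By Fisher's z, a 95% interval around zero is about ±tanh(1.96/√33) = ±0.33 for one arm of 36, against ±tanh(1.96/√68) = ±0.23 for the arm-adjusted coefficient on 72.
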